5.4 Study Design and Study Visits

Subjects who appear to meet entry criteria will review the informed consent (a written description of the purpose, procedures, and risks of the study) with the principal investigator (PI), co-investigator, or study coordinator, and all questions will be answered. The informed consent form will be signed by the subject at the beginning of the screening visit. No protocol-specific procedures will be performed until the subject has signed and dated an informed consent form. This includes the screening procedures.

The enrollment visit should occur within 90 days of the screening visit. However, it is preferred that the enrollment visit occur within 28 days of the screening visit to avoid repeating procedures.

All follow-up study visits will occur within 10 business days of their designation (e.g. week 12 will occur +/- 10 business days from the week 12 timepoint).

		Visit							
Study Procedure	Procedure details	Screen V1	Enroll V2	Surgery V2A	Wk 12 V3	Wk 24 V4	Wk 36 V5	Wk 48 V6	Wk 52
Medical history	 Complete medical history 	•							
Physical examination	Physical exam	•			•	•	•	•	
Documentation of GER	 Symptom questionnaire 	٠				•		•	Р
Assessment of esophageal motility and pH	> pH and manometry	•+				•&			H O N
Laparoscopic anti- reflux surgery *				•					Е
Bronchoscopy *				•				•^	V
Spirometry (Hand-held)									I S
Spirometry (Office based)		٠	•#		•!	•!	•!	•!	I T
DLCO			•		•!	•!		•!	
Arterial blood gas		•			•	•		•	
6 minute walk test		•	●#		•	•		•	
HRCT			•@					•	
Patient reported outcomes	 UCSD SOBQ Cough VAS SGRQ ICECAP EQ-5D 		•		•	•	•	•	
Blood collection			•		•	•	•	•	

Table 1. Table of Study Visits

* These procedures will be performed only in those subjects randomized to surgery.

+Does not need to be completed if done within 6 months of V2 at the study site in accordance with the study protocol.

@ Does not need to be completed if done within 3 months of V2 at the study site in accordance with the study protocol.

Only performed if V2 performed > 28 days after V1.

^ This is an optional procedure and will only be performed if the subject has consented for it.

! If a subject has undergone fundoplication surgery (regardless of treatment assignment) within 8 weeks of this visit date, the subject should not undergo this procedure.

& The pH and manometry should be done a minimum of 12 weeks after surgery, and only in those subjects randomized to surgery.

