will undergo preapproval for billing the laparoscopic anti-reflux surgery and related activities and tests to the subject's insurance (all other study procedures will be paid for by the study). In the unlikely event that a randomized subject is denied authorization, the subject will not have surgery but will be followed on an intention to treat basis. All subjects in the surgical arm will receive a bronchoscopy at the time of surgery. Bronchoscopy is a separate procedure from the surgical intervention. Bronchoscopy will be performed according to standardized protocol and samples (BAL and endobronchial brushings) will be collected. These patients will then undergo surgery according to study protocol (see section 8). They will have a post-operative visit with the surgeon at approximately 2 weeks to ensure appropriate recovery.

Subjects randomized to no surgery will be followed clinically. If there is evidence of significant disease progression (defined by a relative decline in FVC of \geq 10% over 24 weeks or longer), these patients will be allowed to undergo laparoscopic anti-reflux surgery as part of the clinical trial. These patients will otherwise complete the study visits as scheduled.

All subjects in the study will be provided with a home spirometer and instructed to perform spirometry daily throughout the course of the clinical trial. Subjects who are randomized to surgery will be instructed to halt daily spirometry from the date of their surgery until they return to the site for the week 12 visit.

Subjects will be blinded to the results of the home spirometry measurements. Subjects will be instructed to bring home spirometers to each study visit so that data can be downloaded and sent to the DCC for databasing. Subjects will have the option after study completion to keep the home spirometer for personal use.

Safety assessments: Subjects will be contacted by telephone for safety assessments in months where no study visit occurs (months 1, 2, 4, 5, 7, 8, 10, 11) and at week 52. The calls should visits will occur within 10 business days of their designation (e.g. month 1 will occur +/- 10 business days from the month 1 timepoint). One month is defined as 28 days. These phone calls will involve confirming the subject's vital status and asking questions about serious adverse events or adverse events related to the surgical procedure, for subjects randomized to surgery.

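### The home-spirometry halt and the surgical adverse-event phone question follow the randomised arm, so controls operated on within the trial get neither, and a late-operated surgery-arm subject can restart home testing under 8 weeks after surgery

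*Combined protocol and SAP*

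**What the plan says.** All of the following is in section 5.4 of the combined protocol and SAP unless stated otherwise.

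- **Default.** Every subject receives a home spirometer and is "instructed to perform spirometry daily throughout the course of the clinical trial".
- **The one exception.** Subjects randomized to surgery are "instructed to halt daily spirometry from the date of their surgery until they return to the site for the week 12 visit".
- **Surgery for controls.** If a control's FVC falls by at least 10% (relative) "over 24 weeks or longer", "these patients will be allowed to undergo laparoscopic anti-reflux surgery as part of the clinical trial". Their visit schedule otherwise stays the same.
- **Safety calls.** Calls take place in months 1, 2, 4, 5, 7, 8, 10 and 11 and at week 52. They cover serious adverse events and "adverse events related to the surgical procedure, for subjects randomized to surgery".
- **Office tests.** The footnote marked ! in Table 1 applies to office spirometry and DLCO: "If a subject has undergone fundoplication surgery (regardless of treatment assignment) within 8 weeks of this visit date", the test is not done.
- **Post-operative visit.** For the surgery arm: "They will have a post-operative visit with the surgeon at approximately 2 weeks to ensure appropriate recovery". Section 8 gives a post-operative visit to everyone who is operated on, without a date and with no scheduled study procedures.
- **Reporting.** Section 7.2 makes non-serious events related to the surgery reportable, with no restriction by arm.

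**The concern.** The office-test footnote, the reporting rule in section 7.2 and the post-operative visit in section 8 all depend on whether a subject had the operation. The home-spirometry halt and the surgical phone question depend on the arm to which the subject was randomized. The protocol gives no reason for the difference, and because controls may cross over to surgery the two definitions select different people.

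Two things are at stake. The first is the instruction given to a patient just after fundoplication: daily forced manoeuvres at home during weeks in which the trial will not do spirometry in the clinic. The second is even questioning for Aim 3, the safety of the surgery: one operated group is asked by phone about non-serious surgical events and the other is not.

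Within the surgery arm there is a related timing problem. The halt ends at a fixed study visit, not at a set interval after the operation, and no deadline for the operation is stated.

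**Working it through.** The plan gives no figure on this point to reproduce, so the check is calendar arithmetic.

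**Inputs (section 5.4 and Table 1).** The week 12 visit may fall 10 business days either side of its date. The office restriction lasts 8 weeks. A call month is 28 days. Assumptions: study weeks count from enrolment; 10 business days are 2 calendar weeks; adherence to daily testing is full; a control's 24 weeks run from the trial baseline.

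**1. Operated control.** No halt applies. Sessions in the 8 weeks after surgery: 7 × 8 = 56. All of them fall before week 48 if surgery is by week 40. If the post-operative visit comes at about 2 weeks, as stated for the surgery arm, 7 × 2 = 14 sessions precede it. The existing halt cannot be read across to these patients: it ends at the week 12 visit, and a control qualifies from about week 24.

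**2. Surgery arm.** Let surgery be at week s and the week 12 visit at week v, with v = 10, 12 or 14.

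- Halt length = v − s weeks.
- It is shorter than 8 weeks when s > v − 8, that is, after week 2, 4 or 6.
- Home sessions inside 8 weeks of surgery = 7 × max(0, 8 − (v − s)).

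| Surgery at week | v = 10 | v = 12 | v = 14 |
|---|---|---|---|
| 2 | 0 | 0 | 0 |
| 4 | 14 | 0 | 0 |
| 6 | 28 | 14 | 0 |
| 8 | 42 | 28 | 14 |

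For surgery at week 10 with v = 12: 7 × (8 − 2) = 42. If surgery falls after the week 12 visit, the halt has no end point at all.

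Late surgery is possible on the text. Pre-operative work-up and insurance approval follow randomization. The Table 1 footnote marked & requires pH testing, scheduled at week 24, to be at least 12 weeks after surgery, which is compatible with surgery up to about week 24 − 12 = 12. The ! footnote is itself attached to the week 12 visit.

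**3. Safety calls.** Months 1, 2, 4, 5, 7, 8, 10 and 11 are weeks 4, 8, 16, 20, 28, 32, 40 and 44. A control who meets the trigger at week 24 has at most 4 monthly calls left (28, 32, 40, 44), plus week 52. At week 36 it is 2 (40, 44), plus week 52. On each, the surgical question is not required. I read the arm restriction as applying to the surgical question only, so that serious events are asked of everyone.

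The hand-held spirometry row of Table 1 shows no marks in the text available to me. Nothing above rests on it.

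**The case against.** The strongest reply is that the 8-week benchmark is borrowed. The ! footnote sits on the office spirometry and DLCO rows and is worded around a visit date; nothing sets an 8-week rule for the hand-held device. That is correct. A reader might infer that early home testing breaches the protocol, or that it is known to be unsafe. The documents support neither: the halt's purpose is not stated, and what can be shown is that two rules about similar tests disagree.

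A reader might also infer that operated controls drop out of surgical safety capture. They do not. Their surgical events are reportable under section 7.2, section 8 gives them a post-operative visit, they attend the remaining visits, and outstanding events are updated at week 52. Only the active phone question is missing, so no loss of Aim 3 data can be asserted.

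Nor does the point reach the results. Section 10.2 uses FVC at baseline and every 12 weeks and leaves out operated controls' post-surgical values. No endpoint in section 6 or analysis in section 10 uses home readings.

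Finally, the counts are ceilings. They assume full adherence, and the call count assumes surgery as soon as the trigger is met. For surgery by week 4 with the visit on time, the surgery-arm count is zero. When surgery precedes the week 12 visit, the restart happens at a visit that includes a physical examination, so it is not unsupervised. All of this stands and keeps the severity low. It does not remove the instruction to an operated control to go on testing daily.

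**Conclusion.** The point holds as a drafting inconsistency of minor severity. Two rules in section 5.4 are tied to the arm where the comparable rules are tied to the operation. Followed literally, an operated control has up to 56 home sessions in the 8 weeks when office spirometry and DLCO are withheld, and misses the surgical question on at most 4 monthly calls plus week 52. A surgery-arm subject operated on after about week 4 (week 2 to 6 over the visit window) restarts home testing less than 8 weeks after surgery.

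The figures rest on weeks counted from enrolment, full adherence, and a control trigger no earlier than about week 24. How many subjects are affected is unknown, because the protocol gives neither a surgery deadline nor an expected number of operated controls. A manual of procedures might say more, but it is not among the documents. Sample size, power and the primary analysis are unaffected.

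**What to change.** **Home spirometry, section 5.4.** Replace the halt sentence with: *Any subject who undergoes laparoscopic anti-reflux surgery during the trial, in either arm, will halt daily home spirometry from the date of surgery until the first study visit at least 8 weeks after surgery (for subjects randomized to surgery, not before the week 12 visit).*

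**Safety calls, section 5.4.** Replace the arm restriction on the surgical question with: *for any subject who has undergone the surgery*.

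**Cost.** One call-script line, perhaps a few more adverse-event reports, and some home readings not taken. With visits on their nominal dates:

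- Surgery arm, operated on at week 2 or 4: no change (halt of 10 or 8 weeks).
- Surgery arm, operated on at week 6, 8 or 10: the halt runs to week 24, not week 12, so 7 × 12 = 84 further readings are not taken.
- Operated control: 56 readings if a visit falls exactly 8 weeks after surgery (for example, surgery at week 28 and visit at week 36). If the next visit comes too soon the number is larger: surgery at week 30 means restarting at week 48, 7 × 18 = 126. After surgery later than week 40, no scheduled visit through week 48 is late enough, so home testing would not restart.

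No present halt is shortened, and no listed endpoint loses data. If the home series is valued for other reasons, the site could instead clear the restart by phone at 8 weeks. The further loss is then 14, 28 or 42 readings for surgery at week 6, 8 or 10, and up to 56 per operated control.

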5.5 Travel Reimbursement

Subjects participating in this study will be eligible to receive up to \$250 per study visit for covered costs associated with travel to study visits. Covered costs may include:

- Mileage (round-trip from the subject's home address to the study clinic)
- Parking fees at the study clinic
- Airfare to and from the study clinic
- Hotel costs
- Taxi fare

Sites will reimburse subjects as necessary, and submit documentation of payment to the Data Coordinating Center for reimbursement of these expenses.

Subjects who are screened and enrolled on consecutive days and stay overnight for these visits can be reimbursed for two study visits (screening and enrollment) – up to \$500.

5.6. Recruitment Procedures

Subjects recruited for this study will be physician-referred or self-referred to centers participating in this study.

Clinical center subjects previously diagnosed with IPF will be notified of the trials by mail whenever possible.

Recruitment of minorities and women will be monitored by the Data Coordinating Center (DCC) and Data and Safety Monitoring Board (DSMB). If necessary, additional recruitment efforts will be made at specific centers to ensure that the aggregate subject sample contains appropriate representation of women and minorities.

6. Study Endpoints

6.1. Primary Endpoint

The primary endpoint of this study will be the change in FVC (in liters) from baseline to week 48.

6.2. Secondary Endpoints

The secondary endpoints of this study will be:

- Disease progression
- Categorical change in FVC
- Acute exacerbation
- Non-elective hospitalization
- Mortality
- Time to disease progression
- Time to categorical change in FVC, acute exacerbation, or death (composite endpoint)

- Time to non-elective hospitalization or death (composite endpoint)
- Change in UCSD SOBQ score (continuous and categorical)
- Change in SGRQ score (continuous and categorical)
- Change on cough visual analog scale (VAS)
- Change in ICECAP-O score (continuous and categorical)
- Change in EuroQOL EQ-5D scores (continuous and categorical)
- Change in 6-minute walk distance (6MWD) (continuous and categorical)
- Reduction in acid GER by serial pH testing and GER questionnaire
- Quantitative change in HRCT fibrosis score and honeycombing

6.3. Definition of Disease Progression

Disease progression is defined as one or more of the following: relative decline in FVC of \geq 10%; increase in UCSD SOBQ of \geq 5 points; suspected or definite acute exacerbation; death. Subjects and their treating physician will be notified of disease progression documented during the course of the study.

6.4 Definition of Acute Exacerbations

Both definite and suspected acute exacerbations of IPF will be identified. The following 4 criteria will define definite AEx in subjects with acute exacerbation of IPF:

- 1. Unexplained worsening or development of dyspnea within 30 days
- 2. High-resolution computed tomography with new bilateral ground glass abnormality and/or consolidation superimposed on a background UIP pattern
- 3. No evidence of pulmonary infection by endotracheal aspirate or bronchoalveolar lavage.
- 4. Exclusion of alternative causes including heart failure, pulmonary embolism, or an identifiable cause of acute lung injury.

Idiopathic acute respiratory worsening thought to represent acute exacerbation but failing to meet one or more criteria will be classified as suspected acute exacerbations.

6.5 Method for Identification of Acute Exacerbation

All subjects will be educated regarding the importance of identifying AEx. At the time of enrollment, subjects will be educated to the possibility of developing acute symptomatic worsening that might represent an AEx of IPF and instructed to contact their study site coordinator within 48 to 72 hours of the apparent event. All subjects will be questioned about any change in dyspnea or cough at any interim clinic visits or hospitalizations.

All respiratory worsenings will be identified and classified by site investigators utilizing the following template:

- -- Community/hospital acquired pneumonia
- -- Bronchitis
- -- Aspiration pneumonitis
- -- Pulmonary embolism
- -- Pneumothorax
- -- Unknown cause
- -- Non-pulmonary cause (e.g. anxiety)

If "unknown cause" is selected by the site investigator, further categorization as follows will be required:

- -- Definite acute exacerbation (meets protocol criteria in section 6.4)
- -- Suspected acute exacerbation as defined in section 6.4.

-- Unclassifiable

An AEx will be treated at the discretion of the treating physician.

7. Policies and procedures for identifying, reviewing, and reporting adverse events

7.1 Definitions

Adverse event (AE) means any unfavorable medical occurrence in a human subject, including any abnormal sign (for example, abnormal physical exam or laboratory finding), symptom, or disease, temporally associated with the subject's participation in the research.

Serious adverse event (SAE) means any event temporally associated with the subject's participation in research that meets any of the following criteria:

- results in death;
- is life threatening (places the subject at immediate risk of death from the event as it occurred);
- requires inpatient hospitalization or prolongation of existing hospitalization;
- results in a persistent or significant disability/incapacity

In addition, important medical events that may be considered an SAE if they require medical or surgical intervention to prevent one of the outcomes listed above.

An Unexpected SAE is an SAE that the nature or severity of which is not expected from the disease or interventions within the clinical trial.

An AE Associated with Research means there is a reasonable possibility that the AE may have been caused by the interventions (including tests) in the clinical trial.

7.2 Reporting

SAE Reporting - All deaths and all SAEs require reporting from the start of randomization to week 52. Any ongoing SAEs as of week 52 should be followed to resolution. The research staff at the site where the subject is seen is required to contact the coordinating center to inform them of the SAE within 1 business day of knowledge of the event. The site should also submit an SAE form via the eCRF system within 1 business day of knowledge of the event.

The clinical center investigator will provide an assessment of causality of the event to the study intervention (i.e. is it an SAE associated with research) based upon the information available at the time of the report. It is understood that complete information about the event may not be known at the time the initial report is submitted, though investigators should make every effort to obtain information. All events submitted without a causality assessment

will be considered "associated with research" until a clarification is made. The investigator must also sign each SAE form.

The clinical center investigator must enter follow-up information (e.g., diagnosis, outcome, and results of specific investigations) as it becomes available. Follow-up should be submitted according to the same process used for reporting the initial event as described above (i.e. within 1 business day of knowledge). All SAEs will be followed until resolution, stabilization, or the event returns to baseline condition or value, whichever occurs first. Investigators are responsible for reporting SAEs to their local IRB in accordance with local guidelines. The coordinating center will be responsible for tracking all SAEs, performing a clinical review of the SAE data, querying the clinical centers for additional data, and following unresolved SAEs.

AE Reporting

This study intends to capture information on all serious adverse events, acute exacerbations as described in section 6.5, as well as non-serious adverse events related to the surgical intervention. Non-serious, non-surgery related adverse events should not be reported.

The DCC will submit a detailed report of pre-specified AEs of interest and all SAEs monthly to NHLBI and DSMB chair. In addition, each SAE will be reported to NHLBI and DSMB chair by DCC within one business day after receiving the report. The DSMB Chair will review the information presented and determine if any additional information is needed, and/or a DSMB teleconference should be held. Guidelines for the DSMB procedures will be detailed in the DSMB charter.

8. Surgical Intervention

Subjects randomized to laparoscopic anti-reflux surgery will undergo preoperative evaluation by the surgical team after randomization. This will include a standard preoperative surgical assessment, anesthesia clearance, and other testing as medically indicated. During surgery, standard American Society of Anesthesiologists protocols will be used to monitor patients under general anesthesia. All subjects will be mechanically ventilated using the minimal tidal volumes and supplemental oxygen required to maintain adequate gas exchange. All subjects who undergo laparoscopic anti-reflux surgery will have a post-operative visit to insure appropriate recovery. There will be no scheduled study procedures during this visit.

Laparoscopic anti-reflux surgery generally involves the following steps. Individual patient issues may require modifications depending on the surgeon's intraoperative assessment. All efforts will be made to adhere exactly to the same surgical procedure, but if needed, the surgical team can deviate from the standardized protocol to ensure the safety of the patient and to achieve maximum beneficial results. Completion or modification of each stage will be documented in the clinical research form.

Step 1: Division of gastrohepatic ligament; identification of right crus of the diaphragm and posterior vagus nerve.

Step 2: Division of peritoneum and phreno-esophageal membrane above esophagus; identification of the left crus of diaphragm and anterior vagus nerve.

Step 3: Division of short gastric vessels.

Step 4: Creation of a window between gastric fundus, esophagus, and diaphragmatic crura.

Step 5: Placement of Penrose drain around the esophagus.

Step 6: Closure of crura.

Step 7: Insertion of the bougie into esophagus and through esophageal junction.

Step 8: Wrapping of gastric fundus around lower esophagus.

Step 9: Final inspection, removal of instruments and trocars from the abdomen, and closure of the port sites.

9. Data Management

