2.1. Study Hypothesis

Our primary hypothesis is that the reduction of abnormal GER with laparoscopic anti-reflux surgery will slow the progression of IPF as measured by FVC. We further hypothesize that laparoscopic anti-reflux surgery will reduce the frequency of acid reflux, will be safe and well tolerated, will improve symptoms and quality of life, and will reduce the incidence of acute exacerbation, hospitalization, disease progression and death. Specifically, we will address the following aims:

2.2. Specific Aim 1

We aim to determine the impact of laparoscopic anti-reflux surgery on change in FVC over 48 weeks in patients with IPF and abnormal GER.

2.3. Specific Aim 2

We aim to correlate the reduction in acid reflux events with the change in FVC over 48 weeks in patients with IPF and abnormal GER.

2.4. Specific Aim 3

We aim to determine the safety of laparoscopic anti-reflux surgery in patients with IPF and abnormal GER.

2.5. Specific Aim 4

We aim to explore the impact of laparoscopic anti-reflux surgery on key secondary endpoints over 48 weeks in patients with IPF and abnormal GER.

2.6. Specific Aim 5

To identify molecular markers of IPF disease activity and gastroesophageal reflux in biological samples from patients with IPF and abnormal GER.

3. Background and Significance

Idiopathic pulmonary fibrosis (IPF) is a chronic progressive lung disease of unknown cause and increasing prevalence in the United States.^{1,2} An estimated 100,000 Americans will die from IPF this year, and aside from lung transplantation, which only 1% will receive, there is no FDA-approved therapy.

Over the last decade, a potential role for gastroesophageal reflux (GER) in the progression of IPF has been suggested.³ This is based on several observations: First, it is clear that the overwhelming majority of patients with IPF have abnormal GER.⁴⁻⁶ Second, small case series of patients with IPF treated for GER demonstrated stabilization of pulmonary physiology and oxygenation.^{7,8} Third, the treatment of GER has been associated with improved survival in two large, independent retrospective cohorts of patients with IPF.⁹

Importantly, there are no prospective, randomized data addressing the treatment of GER in IPF and there is a real chance that the data collected to date are misleading. A prospective, controlled trial is essential to answer this question.

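### New deaths and SAEs stop being reportable at week 52 from randomisation, so controls who cross over to trial surgery late have little or no capture of new post-operative events

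*Combined protocol and SAP*

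**What the plan says.** - **Reporting window (Section 7.2).** "All deaths and all SAEs require reporting from the start of randomization to week 52". The one extension is for events already open: "Any ongoing SAEs as of week 52 should be followed to resolution". The same section intends to capture non-serious AEs related to the surgery, without restricting this to one arm.
- **Control-arm surgery (Section 5.4).** The trigger is a relative FVC decline of at least "10% over 24 weeks or longer". When it is met, "these patients will be allowed to undergo laparoscopic anti-reflux surgery as part of the clinical trial". These subjects otherwise keep their original visit schedule. No last date is given.
- **Contacts (Section 5.4).** Office visits are at weeks 12, 24, 36 and 48, each within 10 business days. Telephone safety calls fill the other 28-day months, with a final contact at week 52 or 4 weeks after the last visit. The call's question on surgical AEs is worded for those randomised to surgery.
- **Post-operative visit (Section 8).** Every operated subject has one, but "There will be no scheduled study procedures during this visit".
- **Aim 3 (Section 2.4).** "We aim to determine the safety of laparoscopic anti-reflux surgery in patients with IPF and abnormal GER".

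**The concern.** The operation is the exposure whose safety Aim 3 is meant to establish, yet every safety clock in the protocol starts at randomisation. For a subject operated soon after randomisation this makes little difference. For a control who crosses over late, the window may close shortly after the operation, or before it if work-up takes time.

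Late surgery is foreseen. A footnote to Table 1 omits spirometry and DLCO at any visit within 8 weeks of fundoplication, whatever the assigned arm, and it is attached to the week-48 visit. The protocol thus provides for operations between weeks 40 and 48 without a matching safety period.

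Two things are at stake. First, new deaths and SAEs after a late crossover operation would not have to be reported, and these patients were selected for a documented FVC loss. Second, Section 5.4's call wording and Section 7.2's reporting intent do not agree on whether operated controls are asked about surgical AEs at all.

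**Working it through.** **Inputs from the documents.** Reporting closes at week 52 (Section 7.2). Spirometry visits at which a decline over at least 24 weeks from baseline can be found are weeks 24, 36 and 48 (Section 5.4). The visit window is 10 business days, about 2 weeks. There are about 58 subjects at 1:1, so 29 controls. Table 3's figure of 58 reproduces: a two-sample t-test at 0.8 SD, two-sided 0.05 and 80% power needs 26 per arm, and 52 / 0.9 = 57.8, rounded up to 58. The point does not depend on that figure.

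**Assumption.** The documents give no interval from trigger to operation, so a delay *d* of 0 to 12 weeks is shown.

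**Step 1: weeks of new-event reporting left after surgery** = max(0, 52 − (trigger week + *d*)).

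| Trigger | d = 0 | d = 4 | d = 8 | d = 12 |
|---|---|---|---|---|
| Week 24 | 28 | 24 | 20 | 16 |
| Week 36 | 16 | 12 | 8 | 4 |
| Week 48 | 4 | 0 | 0 | 0 |
| Week 48 visit held 2 weeks late, close fixed at week 52 | 2 | 0 | 0 | 0 |
| Surgery arm (delay from randomisation) | 52 | 48 | 44 | 40 |

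A week-48 qualifier has no reporting time left once the delay reaches 52 − 48 = 4 weeks.

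**Step 2: planned contacts left.** Visits and calls together fall every 4 weeks up to week 52. After an operation at weeks 48 to 51, one contact remains (week 52). After an operation at week 52 or later, none remains.

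**Step 3: do other provisions close the gap?**
- Follow-up of open SAEs needs an event that began by week 52.
- The long-term contact in Section 5.4 is optional, unscheduled and not described as safety follow-up.
- The post-operative visit has no scheduled data collection. An SAE learned of there is reportable, but only while the Section 7.2 window is open.

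**Step 4: how many controls might be affected?** The documents do not say. Assumptions: mean control decline 0.15 to 0.25 L over 48 weeks, linear in time; SD of observed 48-week change 0.25 L; baseline FVC 2.0 to 3.0 L; measurement noise 0.10 L per visit; trigger judged against baseline. Simulated numbers first qualifying, of 29:

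| First qualifying visit | Controls |
|---|---|
| Week 24 | 2.7 to 9.5 |
| Week 36 | 3.5 to 6.1 |
| Week 48 | 3.2 to 4.3 |

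If 0.25 L is instead the SD of the true slope before noise is added, the lower end at week 48 is 2.9. These are counts of eligibility. Death, withdrawal, refusal, payer denial or surgical unsuitability would all reduce the number operated.

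**The case against.** The strongest reply is that the gap is narrow. Much of it stands:

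- **Most qualifiers have a longer ceiling.** Week-24 and week-36 qualifiers can have up to 28 and 16 weeks. Only week-48 qualifiers, and week-36 qualifiers with a long delay, are left with a few weeks or none.
- **Events are not abandoned at week 52.** An SAE that starts in the window is followed to resolution.
- **Surgery after week 52 may be ordinary care.** Participation lasts 52 weeks, and the allowance is for surgery within the trial. The documents do not settle this, so having no cover at all is one reading of the text and not a stated outcome.
- **The post-operative visit does not suppress reporting.** SAE reporting depends on the site's knowledge of the event, not on a study procedure.

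A reader might also infer that surgery-arm subjects share the problem because no surgical deadline is written. The schedule points the other way. Table 1 places surgery between enrolment and week 12, home spirometry is halted from surgery to the week-12 visit, and week-24 pH testing carries this condition: "The pH and manometry should be done a minimum of 12 weeks after surgery". That implies surgery by about week 24 − 12 = 12, which leaves about 40 weeks or more.

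A reader might further infer that the safety record will be biased in favour of surgery. The documents do not say how Aim 3 will be analysed or whether crossover operations are pooled. A common window from randomisation is also a normal basis for comparing arms. What can be shown is incompleteness, not its direction or size.

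None of this supplies a safety period for the late-operated control, and the mismatch over who is asked about surgical AEs remains.

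**Conclusion.** The point holds for late crossovers. Reporting of new deaths and SAEs closes at week 52 from randomisation, while surgery for controls within the trial has no last date and no safety period of its own. The arithmetic for the ceilings uses only the documents' dates; how far actual cover falls below them depends on the unstated delay to surgery.

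The practical size is small in numbers: the simulated counts for weeks 36 and 48 rest on assumed FVC behaviour and overstate the operations that would follow. With about 29 subjects per arm, however, one or two unreported operative SAEs would matter to Aim 3. It would go too far to say that crossover patients in general are unfollowed, or that the DSMB would be shown a falsely favourable picture. The supported conclusion is that the surgical safety record would be incomplete for a few late-operated controls, and that Sections 5.4 and 7.2 need to be reconciled on surgical AEs.

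**What to change.** 1. In Section 7.2, end reporting of deaths, SAEs and surgery-related AEs at the later of week 52 and a fixed interval after any trial anti-reflux operation, in either arm, with the added time covered by telephone. Twelve weeks is offered as an example. It is the reviewer's choice: Table 1 uses that interval only to time pH and manometry testing, not for safety.
2. State whether surgery after week 52 counts as trial surgery for reporting purposes.
3. Reword the safety-call text in Section 5.4 so that every operated subject is asked about surgical AEs, in line with Section 7.2.
4. Report surgical SAEs over all operations, with follow-up time counted from surgery, alongside the comparison by randomised arm.

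The cost is a short amendment and a few extra calls. With a 12-week interval, a control operated at week 48 is followed to week 60, and one operated at week 52 to week 64, so last contact moves by up to 12 weeks (about 3 months). If operations after week 52 are counted, it moves correspondingly further. No treatment rule and no week-48 efficacy data change.
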